**5B1. Procedure.** Parent(s) or legal guardian(s) (hereafter referred to as "parents") of adolescents in the targeted age range will be recruited from the RI Truancy Court Program (see letters of support). Following arraignment procedures, families will be given information about the project by study staff who will be present at all truancy court arraignments and who will also answer any questions parents may have. Interested participants will be contacted by study staff at their second Truancy Court arraignment appointment. During this meeting, they will receive an oral and written description of the study, including a description of the project procedures, number of appointments and compensation for participation, potential risks and benefits, and confidentiality. Families who provide parental consent and adolescent assent will be administered the screening battery. If the child does not meet the substance use and CBCL inclusion criteria, they will be given a package of educational materials regarding truancy and SU.

**Assignment of participants to conditions.** In the open trial portion, the first 20 families will receive the IMI/FCU in order to inform adaptations to the current protocol and to examine its feasibility and acceptance. After this open trial, 100 families will be recruited and randomized into either the experimental or the comparison control condition. These assignments will be made soon after completing the baseline assessment and through random assignment using the urn method (Stout et al., 1994). Urn randomization assigns participants in a given subgroup to intervention conditions, but systematically biases the randomization in favor of balance among the intervention conditions. Participants will be randomized according to gender, substance abuse (yes or no), and meeting CBCL cut-off for internalizing only versus externalizing only or externalizing/internalizing.

**5B2. Baseline and follow-up assessments (IMI/FCU and PE).** Parents and teens will complete the

assessment battery described below at their local school. In person follow-up assessments will be held at 3 and 6 months following the baseline assessment. An RA who will be blind to condition assignment will conduct each follow-up assessment. The follow-up assessment battery will be identical to baseline.

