All FAsTask videos will be coded by the Treatment Provider and the PI or Co-I, who will watch each segment of the videotape together and complete separate coding sheets. Ratings assigned to the family will then be discussed and consensus will be reached. When consensus cannot be achieved, the PI will review the tape segment to determine the coding. Ratings reached by consensus will be used during the feedback session. "Macro" clinical scores are calculated and coded as an area of "strength," "needs improvement," or "challenge," and provided as feedback during the Family Check-up session. Macro scores include positive relationships, monitoring, limit setting, problem solving, school importance and substance use norms. Norms were derived from 120 multi-ethnic families whose children had good school attendance and no disruptive problems in school (Dishion & Kavanagh, 2003). This coding method was used in Project REFRAME with 79 families and has been found to be the most effective method for coding the task for the purposes of providing feedback to families. These data along with parent self-report measures (see [Table 2](#)) will be used to generate the individualized feedback report for use in the parent feedback session.

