**5C3. Fidelity to Interventions** The PI, Co-I and a masters-level clinician will serve as the counselors for this project and will first run 20 families before the randomization phase. In this proposal, Drs. [name] and [name] will train and supervise counselors and [name] will evaluate fidelity on a real time basis and provide feedback. After training, counselors will receive weekly supervision by Drs. [name] and [name]. Adherence to the IMI/FCU feedback session will be evaluated using two methods. First, the individual MI and FCU will be audiotaped as will the PE condition. The MI will be rated for both IMI/FCU adherence and competency. The first 10 sessions of each counselor and 50% of randomly selected session tapes thereafter will be coded by the Co-I [name] to objectively evaluate clinician competence in using MI techniques as well as adherence to the IMI or FCU protocol. Criteria for adherence are defined in terms of specific content areas, as well as adherence to basic MI principles outlined in the IMI and FCU manuals (see Appendices 3 & 5 for IMI and FCU fidelity ratings). We have developed a system for assessing adherence, which includes a measure both of the degree to which counselors adhere to stylistic and strategic imperatives of MI and the degree to which they adhere to the protocol itself (Barnett et al., 2001; Monti et al., 1999). This information is incorporated into supervision. These procedures are identical to those used successfully in our current project. Second, following the IMI and FCU sessions the counselor and the adolescent/parent will separately complete an adherence rating form that will indicate the extent to which the counselor engaged in the behaviors consistent with IMI/FCU and those required by the intervention protocol; both will include length of time of the session. These forms will be reviewed by the PI, and clinical training will be tailored to project clinicians, as needed. This will provide data for evaluating both the fidelity and the quality of the IMI/FCU from the perspective of both the participant and the counselor. We have used this system in our two previous and current adolescent studies with success. The PE condition will be rated using the IMI adherence sheet to ensure that none of the MI techniques are used in the PE condition.

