## 1. Background Variables

**Demographics.** Routine socio-demographic variables will be recorded including age, gender, race, school status, and history of mental health or substance use treatment. Locator information is also collected.

Table 2. Measures	Parent/Adol	Baseline	3 mos.	6 mos.
1. Background Demographics Locator Information	A/P A/P	X X	X	
2. Substance Use Parent Substance Use Adolescent Drinking Questionnaire (ADQ) Drug Use Questionnaire Timeline Follow-Back – Substance Use	P A A A	X X X X	X X X X	X X
3. Family Management Parent Monitoring Questionnaire (PMQ) Parent Reactions to Youth AOD Use Parent-Adolescent General Communication Scale Parent-Adolescent Alcohol and Drug Communication Scale Parent-Adolescent Sexual Communication Scale Conflict Behavior Questionnaire (CBQ) Video Code – Parent Limit Setting and Monitoring	A/P P A/P A/P A/P A/P A/P	X X X X X X X	X X X X X X X	X X X X
4. Other Problem Behaviors Child Behavior Checklist (CBCL) Reckless Behavior Questionnaire (RBQ) School Attendance - TLFB School Truancy and Performance Sexual History/Perceived Risk of HIV/STDs	P A A A A	X X X X X	X X X X X	X X X X X
5. Peer Influences Peer Use/Tolerance of Use Parental Management of Peers (PMPI) Peer Social Skills (Child) Peer Social Skills (Parent)	A A A P	X X X X	X X X X	X X X X
6. Teen Cognitions Marijuana Effect Expectancy Questionnaire Motivation to Abstain and Perceived Difficulty - Marijuana Youth Alcohol and Drug Survey Subscales Brief Situational Confidence Questionnaire	A A A A	X X X X	X X X X	X X X X
7. Substance Use and Mental Health Treatment History(CASA)	P	X	X	X
8. Intervention Acceptability Exit Interviews Session Evaluation Form	P P	X a X a		
9. Family Check-Up Only Measures Parent Substance-Related Beliefs Family Stress (on PSSC) House Rules Questionnaire Parent Support-Questionnaire FAsTask Video (10 tasks)	P P P P P/A	X X X X X		

aAdministered after 2-session intervention

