Conflict Behavior Questionnaire (CBQ). The CBQ (Robin & Foster, 1989; Prinz, Foster, Kent, & O'Leary, 1979) measures perceived conflict and negative communication in the family in the two to three weeks preceding the assessment session. Parallel forms are completed by the adolescent and the parent. In two parent families, the adolescent completes two CBQ's, one with reference to each parent. Each form yields an appraisal of the other, and an appraisal of the relationship between the respondent and the other.

FAsTask Video Code. The FAsTask (described previously) provides an in vivo assessment of parenting behaviors and parent-child relationships. We limited the video assessment to 3 tasks (Problem-solving truancy, substance use norms and risk behavior norms) because these are the primary outcomes examined in this application. We also tried to limit reactive effects by limiting the number of tasks. The first follow-up is 3 months after the baseline assessment, so any reactive effects are likely to be small.

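### No masked coder is named for the follow-up family videos, and the only coding rule in the plan gives the tapes to staff who also serve as counselors

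*Combined protocol and SAP*

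**What the plan says.** - **Who codes.** Section 5C1, under FAsTask Clinical Coding: "All FAsTask videos will be coded by the Treatment Provider and the PI or Co-I". The two coders view each segment together, fill in separate sheets and then agree a rating. If they cannot agree: "When consensus cannot be achieved, the PI will review the tape segment to determine the coding".
- **Who delivers treatment.** Section 5C3: "The PI, Co-I and a masters-level clinician will serve as the counselors for this project".
- **Use as an outcome.** Table 2 lists "Video Code – Parent Limit Setting and Monitoring" under Family Management, apart from the block of measures used only for the Family Check-Up, where the 10-task FAsTask appears. Section 5B2 adds: "The follow-up assessment battery will be identical to baseline".
- **Rank.** Section 5D, FAsTask Video Code, limits the outcome video to three tasks "because these are the primary outcomes examined in this application". The Study Design section puts improved family management in the primary hypothesis beside substance use. Section 5e (Aims 2-4) lists family management as a potential mediator, Aim 4a.
- **Blinding.** Section 5B2: "An RA who will be blind to condition assignment will conduct each follow-up assessment". Section 5C1 has Treatment Providers run the FAsTask partly to keep that RA blind. No other masking is described.

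**The concern.** A blind RA protects what the RA collects. A video score is produced later, by whoever rates the tape, so the RA's blindness does not carry over to it. The rating calls for judgment, and the only raters named are people who deliver, supervise or evaluate the intervention sessions. If they also score the 3- and 6-month tapes, their expectations can create or enlarge a difference between arms.

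This matters for two reasons. The rationale in section 5D gives in vivo assessment to both groups because self-report may miss changes in parenting, so the video is meant to be the check on the questionnaires. And sections 5e and 5f say that the trial's main product is effect sizes for planning a larger study. A coding bias goes straight into such an estimate, whether or not a test is significant.

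**Working it through.** **Step 1: the text, side by side.**

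| Question | What the plan gives |
|---|---|
| Who codes tapes? | Treatment Provider with PI or Co-I; the rule covers all tapes (5C1) |
| Do they treat families? | Yes: PI, Co-I and a masters-level clinician are the counselors (5C3) |
| Do they see arm-specific material? | Yes: the Co-I codes session tapes "to objectively evaluate clinician competence in using MI techniques as well as adherence to the IMI or FCU protocol" (5C3), and Treatment Providers watch the FAsTask to prepare feedback (5C1) |
| Does the baseline tape itself show the arm? | Very likely: 10 tasks for the Family Check-Up (Table 2), two for PE (Table 1 footnote) |
| Is the video repeated in both arms? | Yes: outcome row in Table 2, and an unchanged battery at follow-up (5B2) |
| Is another coder named, or coding masked? | No, in any section |

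Table 2 is broken in the copy read here, so the 6-month repeat rests on section 5B2.

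**Step 2: reproduce the plan's own power figure.** Inputs from section 5f: 40 per group and a 5% level. The sidedness is not stated; two-sided is taken. For an independent-samples t test with 78 df, the noncentrality is d × √(n/2) = d × √20. At d = .50 this is 2.236 and the power is .598, against .60 in Table 3. The same calculation gives .143, .263 and .424 at d = .20, .30 and .40, against the stated .15, .26 and .42. The method matches.

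**Step 3: false-positive rate under an assumed bias.** Suppose there is no true effect and coders favor IMI/FCU by b points. The spurious effect is d = b/SD, and the rejection rate is the power at that d. The documents give neither b nor an SD, so both are assumptions. The 9-point scale is that of the ratings in the team's current trial (5C1).

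| b (points) | SD (points) | Spurious d | Noncentrality | Rejection rate |
|---|---|---|---|---|
| 0.5 | 2 | .25 | 1.118 | .20 |
| 0.5 | 1.5 | .33 | 1.491 | .31 |
| 1 | 2 | .50 | 2.236 | .60 |
| 1 | 1.5 | .67 | 2.981 | .84 |

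**Step 4: effect on planning.** As an illustration, a true d of .20 plus a bias of .30 would be read as .50. Table 3 then gives 63 per group where 388 would be needed, for a future trial sized on this measure.

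**Step 5: does the quoted agreement protect against this?** Section 5C1 reports agreement of 71% to 96%, mean 86%, counting ratings up to two points apart as agreeing. On a 9-point scale, (9 + 2×8 + 2×7)/81 = 39/81 = 48% of independent uniform ratings would pass. If ratings cluster around the middle with an assumed SD of 2 to 1.5, about 65% to 76% would pass. More basically, agreement at any tolerance cannot show a bias that both raters share.

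**The case against.** A reader might infer that the plan has the counselors score the follow-up outcome of families they coached, and that blinding of the primary outcome is therefore lost. The documents do not support that much.

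- **The coding rule is about feedback.** It stands in the description of the experimental condition, under a heading on clinical coding. Every use it states is the Family Check-Up session, which draws on baseline data. Its scope may be feedback tapes only. The outcome description in section 5D names no coder. This objection stands against any flat statement that counselors code the follow-up tapes. It does not remove the problem: section 5D refers back to the FAsTask as already described, the rule says all tapes, and on the narrow reading the outcome coder is unspecified and still not masked.
- **The rank of the outcome is unsettled.** One sentence calls the video tasks primary. The analysis plan treats family management as a mediator, the power calculation in section 5f is for substance use, and the domain also has six questionnaires that video coding does not touch. This stands. A mediator scored by unmasked staff is still hard to interpret.
- **Knowledge of arm is inferred.** No section links a coding pair to the families they treated. The inference is strong, given the roles in Step 1, but it is an inference.
- **The size is assumed.** The plan supplies no SD and no bias. Two of the three outcome tasks (truancy problem solving and risk behavior norms) are new; their codes are still to be written and their scale is not stated.

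**Conclusion.** The concern holds in a limited form. The plan promises no masked coding for a judgment-based, between-group outcome, and its only coding rule, taken at its word, assigns the tapes to staff who treat families and very likely know their arm. The observed family-management outcome is therefore open to coder bias, and a difference on it could not be told apart from rater expectation.

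The likely size cannot be derived from the documents. Under the assumed SD of 1.5 to 2 points, the range runs from a modest spurious effect (d of .25 to .33 for half a point of leniency) to one as large as the medium effect that section 5f anticipates (d of .50 to .67 for a full point). Self-reported substance use on the TLFB, collected by the blind RA, is not affected. The conclusion does not depend on whether the video is finally ranked as primary or as a mediator.

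**What to change.** 1. In section 5C1, limit consensus coding by the Treatment Provider and the PI or Co-I to the IMI/FCU baseline tapes used for feedback.
2. In section 5D, state that outcome scores come from project staff who deliver no intervention and are masked to arm, for example the blind RA. They score only the segments that both arms perform, at baseline and follow-up, with arm and visit labels removed and segments shuffled across arms and visits. Cutting the tapes to shared segments matters because tape length alone can show the arm.
3. If the RA codes, begin only after all follow-up interviews are complete, so that remarks on tape cannot unblind the TLFB interviews.
4. Use the codebook once the open trial has added codes for the new tasks.
5. In section 5e, state that only masked scores enter between-group analyses.
6. Reconcile the number of video tasks in PE (two in the Table 1 footnote, three in section 5D) and the Table 2 label, which names limit setting and monitoring rather than the three tasks in section 5D. Until this is settled, the shared segments are not defined. State the rank of the video outcome at the same time.

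**Cost.** RA training and coding time. Three 5-minute tasks make 15 minutes per family per visit, so with no attrition 100 families × 3 visits × 15 minutes = 4,500 minutes, or 75 hours of tape. With two tasks it is 100 × 3 × 10 = 3,000 minutes, or 50 hours. To the extent that two staff would otherwise view these tapes together, that time is saved. The losses are routine two-person coding of the outcome tapes and some imperfection in masking: families may mention their sessions, and an RA who has met them may recognize the visit.

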### **5C2. Psychoeducation Condition (PE)**

In the Psychoeducation (PE) condition, participants will complete the same baseline assessment as the IMI/FCU group. In order to control for contact time, families in PE will return for the same number of visits as the IMI and FCU sessions of the IMI/FCU condition. An interventionist will review a set of educational materials with the parents regarding teen SU use, truancy and risk behaviors and parenting a teenager. A similar set of materials will be reviewed with the adolescent (see Appendix 8).

Training (PE). Interventionists in the PE condition will be trained in reviewing psychoeducational materials. A primary goal of training will be to ensure there is no carryover of motivational techniques into the PE condition.

**5C3. Fidelity to Interventions** The PI, Co-I and a masters-level clinician will serve as the counselors for this project and will first run 20 families before the randomization phase. In this proposal, Drs. [name] and [name] will train and supervise counselors and [name] will evaluate fidelity on a real time basis and provide feedback. After training, counselors will receive weekly supervision by Drs. [name] and [name]. Adherence to the IMI/FCU feedback session will be evaluated using two methods. First, the individual MI and FCU will be audiotaped as will the PE condition. The MI will be rated for both IMI/FCU adherence and competency. The first 10 sessions of each counselor and 50% of randomly selected session tapes thereafter will be coded by the Co-I [name] to objectively evaluate clinician competence in using MI techniques as well as adherence to the IMI or FCU protocol. Criteria for adherence are defined in terms of specific content areas, as well as adherence to basic MI principles outlined in the IMI and FCU manuals (see Appendices 3 & 5 for IMI and FCU fidelity ratings). We have developed a system for assessing adherence, which includes a measure both of the degree to which counselors adhere to stylistic and strategic imperatives of MI and the degree to which they adhere to the protocol itself (Barnett et al., 2001; Monti et al., 1999). This information is incorporated into supervision. These procedures are identical to those used successfully in our current project. Second, following the IMI and FCU sessions the counselor and the adolescent/parent will separately complete an adherence rating form that will indicate the extent to which the counselor engaged in the behaviors consistent with IMI/FCU and those required by the intervention protocol; both will include length of time of the session. These forms will be reviewed by the PI, and clinical training will be tailored to project clinicians, as needed. This will provide data for evaluating both the fidelity and the quality of the IMI/FCU from the perspective of both the participant and the counselor. We have used this system in our two previous and current adolescent studies with success. The PE condition will be rated using the IMI adherence sheet to ensure that none of the MI techniques are used in the PE condition.

### **5D. Measures (see Appendix 9 for non-copyrighted measures)**

**Rationale.** The measures for the assessment battery were chosen for three main reasons: first, to provide information and normative data whenever possible that can be used in the feedback portion of the FCU; second, to assess changes in outcomes over time; and third, to assess potential mediators. Although there are a large number of measures, most are brief. With the exception of the measures used specifically for feedback in the FCU (see bottom of Table 2), all measures will be administered to both groups. We felt it was important to conduct some form of dynamic (i.e., *in vivo*) assessment with both groups because changes in parenting behaviors and parent-child relationships are complex and may not be captured by self-report measures alone.

**Screening Measure.** Because teens seen at truancy court are very heterogeneous in their presentation, we will require that all participants meet minimum criteria for internalizing or externalizing disorders on the well-validated Child Behavior Checklist (CBCL). The CBCL (ASEBA: Achenbach & Rescorla, 2001) is a widely-used, parent-rated checklist to assess behavior problems. Well-accepted clinical cut-off scores on the internalizing or externalizing problems of the DSM-oriented scales ( $\geq 70$ ), that are reasonable indicators of youth with diagnosable psychiatric disorders, will be used to screen in for this study. The Timeline Follow Back (described below) will be used to assess the inclusion criterion of 6 or more instances of substance use in the prior 90 days. Teens will also be administered the Schedule for Affective Disorders and Schizophrenia for School- Age Children - Present and Lifetime Version (K-SADS- PL) Substance Use module to rule out substance dependence. The K-SADS-PL (Kaufman et al., 1997) is semi-structured diagnostic interview which

provides an assessment of DSM-IV psychopathology in children and adolescents. Inter-rater agreement on screens and diagnoses is high (range: 93% to 100%). The K-SADS is available at <http://www.wpic.pitt.edu/ksads/default.htm>.

## 1. Background Variables

**Demographics.** Routine socio-demographic variables will be recorded including age, gender, race, school status, and history of mental health or substance use treatment. Locator information is also collected.

Table 2. Measures	Parent/Adol	Baseline	3 mos.	6 mos.
1. Background Demographics Locator Information	A/P A/P	X X	X	
2. Substance Use Parent Substance Use Adolescent Drinking Questionnaire (ADQ) Drug Use Questionnaire Timeline Follow-Back – Substance Use	P A A A	X X X X	X X X X	X X
3. Family Management Parent Monitoring Questionnaire (PMQ) Parent Reactions to Youth AOD Use Parent-Adolescent General Communication Scale Parent-Adolescent Alcohol and Drug Communication Scale Parent-Adolescent Sexual Communication Scale Conflict Behavior Questionnaire (CBQ) Video Code – Parent Limit Setting and Monitoring	A/P P A/P A/P A/P A/P A/P	X X X X X X X	X X X X X X X	X X X X
4. Other Problem Behaviors Child Behavior Checklist (CBCL) Reckless Behavior Questionnaire (RBQ) School Attendance - TLFB School Truancy and Performance Sexual History/Perceived Risk of HIV/STDs	P A A A A	X X X X X	X X X X X	X X X X X
5. Peer Influences Peer Use/Tolerance of Use Parental Management of Peers (PMPI) Peer Social Skills (Child) Peer Social Skills (Parent)	A A A P	X X X X	X X X X	X X X X
6. Teen Cognitions Marijuana Effect Expectancy Questionnaire Motivation to Abstain and Perceived Difficulty - Marijuana Youth Alcohol and Drug Survey Subscales Brief Situational Confidence Questionnaire	A A A A	X X X X	X X X X	X X X X
7. Substance Use and Mental Health Treatment History(CASA)	P	X	X	X
8. Intervention Acceptability Exit Interviews Session Evaluation Form	P P	X a X a		
9. Family Check-Up Only Measures Parent Substance-Related Beliefs Family Stress (on PSSC) House Rules Questionnaire Parent Support-Questionnaire FAsTask Video (10 tasks)	P P P P P/A	X X X X X		

aAdministered after 2-session intervention

